3.4 Study population and groups

Patients with symptomatic knee osteoarthritis requiring TKA will be recruited from the [name] and [name] private rooms at Perth Hip & Knee Clinic. All patients will be screened for eligibility based on the predefined inclusion and exclusion criteria (section 5.1). Patients interested in participating in the study will be provided with an information leaflet and contact telephone number for further information (Appendix 19.7). Details of those patients expressing an interest to participate in the study will be recorded and then be forwarded to the Research Physiotherapist.

The Research Physiotherapist will telephone or meet with the patient to answer any additional queries and confirm whether or not the patient would like to participate in the study. More complex queries will be escalated to the Chief Investigator who will telephone the patient directly to discuss these issues further. Ideally, the time frame from the orthopaedic consultation to the decision to participate in the study will be approximately one week, which will give the patient sufficient time to perform further research, discuss study participation with family and/or friends, and contact the Research Physiotherapist for any additional information. This time frame may be shortened if a patient is agreeable with the study, due to patient flow and appointment availability at the consulting rooms. Contact details of the Research Physiotherapist and Chief Investigator are provided within the patient information leaflet.

If the patient agrees to participate in the study, the Orthopaedic fellow will randomise the patient into one of the two treatment groups. Patients allocated to mFA TKA will form the 'control group' whilst those allocated to kFA TKA will form the 'investigation group'. The method for randomisation is discussed in section 3.6. Written informed consent for both the operative procedure and inclusion into the study will be signed at the preadmission visit (Appendix 19.7). The procedure for obtaining written informed consent is discussed in more detail in section 5.

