3.6 Randomisation procedure

The system for randomisation will be the same throughout the study period and must be strictly adhered to. The following method will be used to allocate a trial patient to either the mFA TKA ('Control group') or to the kFA TKA ('Investigation group').

Randomisation will be carried out using a blocked effect. This method is designed to randomize subjects into two groups that result in equal sample sizes over time. The blocks will be small (n=4), and balanced within the predetermined group assignments, which will keep the number of subjects in each group similar at all times. There will be no stratification factors involved in the randomization as randomization will occur before the trial starts. Using a randomization website (www.random.org), a random number (between 1 and 100000) will be generated. This will form the "seed" number for the blocked randomization process. Using a randomization website (www.sealedenvelope.com) the randomization list will be created. Patients will be allocated in a sequential order of consent, strictly adhering to the allocation of groups. Screen shots of the randomization process and seed number will be taken throughout, and held from the CI to minimize randomization bias. The orthopedic fellow will then privately communicate to the CI the allocated group, to enable alignment and templating planning to be performed using the MAKO software. All patients and clinical staff recording the post operative clinical outcomes of interest will remain blinded to minimize performance and detection bias.

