If the patient initially agrees to participate in the study and then changes his/her mind at a later stage, they are free to do so without any compromise to their further care. If this occurs before obtaining informed consent then the patient's decision will be relayed to the operating surgeon who will discuss suitable options directly with the patient, and organise postoperative follow-up care as per all routine (non-study) patients undergoing TKA at Perth Hip and Knee Clinic. There randomisation number will not be reallocated to the next patient, to ensure the blocks remain concealed. Drop in and out details are in section 6. If the patient agrees to participate in the study and then declines further inclusion after surgery has been performed, then the patient's follow-up care will be arranged as per routine TKA follow up at Perth Hip and Knee Clinic. Patients will be notified that once statistical analysis of the study has been performed, and all patient data has been de-identified for analysis, they will not be able to withdraw their clinical data. Statistical analysis of patients that drop out is discussed in section 6. Following randomisation and informed consent at the preadmission visit, baseline information will be recorded and documented in the Perth Hip and Knee Clinic Socrates database. Data handling and management are recorded in more detail in section 9.

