3.7 Surgical Intervention: MA vs. FA TKA

All patients undergoing TKA will undergo preoperative CT scan of the leg to establish the extent of the disease process, determine bone resection, and plan implant sizing and positioning. The preoperative CT scan will be used to create individualized plans for achieving mechanical and kinematic alignment and stored within the robotic program that is used during the operative procedure. This will ensure that all implants and equipment for achieving either mechanical alignment or functional alignment are ready and available for use in theatre. These

plans will provide the initial point from which functional alignment will be achieved.

Following informed consent and randomisation into one of the two treatment groups, patients will undergo robotic-arm assisted TKA by one of the participating surgeons. Surgery in both groups will be undertaken through the standard anteromedial arthrotomy with positioning of reference pins in the femur and tibia for registration of the hip centre, ankle position and limb alignment. The femur will be prepared first in all operations. Cruciate retaining technique will be used in both groups. Interoperative requirement for a more constrained implant will result in exclusion from the study.

In MA TKA, tibial and femoral osteotomies in the coronal plane will be planned perpendicular to the tibial and femoral mechanical axes respectively to achieve neutral overall alignment. Soft tissue balance will be assessed and minor adjustments to bony alignment made to balance the knees with a maximal adjustment of two degrees valgus and two degrees varus of coronal alignment from neutral. Femoral rotation will be planned to surgical epicondylar axis and adjustments to rotation made to allow equal flexion and extension balance (to within 1mm). If balance can not be achieved within these boundaries then soft tissue release will be undertaken.

In the sagittal plane, 0-3 degrees of posterior tibial slope and 0-5 degrees of femoral component flexion will be used to optimise implant sizing whilst preventing notching. In the axial plane, the tibial component aligned to Akagi's line, which connects the medial border of the patellar tendon attachment to the middle of the posterior cruciate ligament.

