5.0 Consent

Patients with symptomatic knee osteoarthritis requiring TKA will be recruited from the private rooms at Perth Hip & Knee Clinic. All patients will be screened for eligibility based on the predefined inclusion and exclusion criteria (section 5.1) by a member of the clinical team. This includes the Orthopaedic Consultant Surgeon, Clinical Fellow, or Research Physio. If the patient meets the all of the inclusion criteria (section 5.1) and none of the exclusion criteria, and expresses an interest to participate in the study they will be provided with a patient information sheet (Appendix 19.7). This provides details about the study, treatment, follow-up and contact details for further information. All members of the clinical team are familiar with the study and will address any preliminary questions about the study. Details of those patients expressing an interest to participate in the study will be recorded in the patient contact sheet, which will be a password protected excel document that only [name], [name] and [name] will have access to.

One week after this outpatient consultation, the Research Physiotherapist will telephone the patient to answer any additional queries and confirm whether or not the patient would like to participate in the study. If the patient agrees to participate in the study, the Research Physiotherapist will randomise the patient into one of the two treatment groups. Patients allocated to mFA TKA will form the ‘control group’ whilst those allocated to kFA TKA will form the ‘investigation group’. The method for randomisation is discussed in Section 3.6. Written informed consent for both the operative procedure and inclusion into the study will be signed at the preadmission appointment.

The ideal length of time between initial consultation and obtaining informed consent for inclusion into the study is at least 1 week. This method provides time for potential participants to consider the trial and ask questions before written consent for participation is requested. This time may be shortened due to patient flow and clinic appointment availability, as long as the patient is agreeable. Consent will be taken by the study coordinator or by

a designated member of the surgical team who is familiar with the study.

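### Sections 3.4 and 5.0 name different randomisers, and both roles assist with outcome recording described as blinded, so assessor blinding is not secured

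*Combined protocol and SAP*

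**What the plan says.** **Who randomises.** Section 3.4: "the Orthopaedic fellow will randomise the patient into one of the two treatment groups". Section 5.0: "the Research Physiotherapist will randomise the patient into one of the two treatment groups". Section 3.6 does not name the person who draws the allocation, but it says: "The orthopedic fellow will then privately communicate to the CI the allocated group".

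**Who records outcomes.** Section 3.6: "All patients and clinical staff recording the post operative clinical outcomes of interest will remain blinded". Section 3.9 also says that observers are blinded, and then adds that the Research Physiotherapist (RP) and the fellow will help. The GP letter in Appendix 19.3 repeats that observers do not know the group.

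**When.** Sections 3.4 and 5.0 randomise once the patient has agreed, and written consent is signed later, at preadmission. Section 3.6 fits that order. It provides for a patient who changes their mind before consenting, and says of that patient: "There randomisation number will not be reallocated to the next patient". Two other phrases could suggest consent first. Section 3.6 has "Patients will be allocated in a sequential order of consent", and section 3.7 has "Following informed consent and randomisation into one of the two treatment groups".

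**Safeguards.** Section 3.6: "Screen shots of the randomization process and seed number will be taken throughout, and held from the CI to minimize randomization bias". Appendix 19.6 standardises the functional tests with scripted instructions for sit-to-stand, a fixed cradle for the dynamometer and the average of three Lachmeter readings.

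**The concern.** Site staff cannot follow both 3.4 and 5.0. Whichever they follow, the named randomiser is one of the two roles that 3.9 brings into outcome recording. The promise that recorders are blinded then rests on a separation that the text does not describe.

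At stake first are the measurements in which an examiner's expectation can enter: Lachmeter, dynamometer, range of movement, sit-to-stand and the radiographic angles. The Lachmeter reading, for example, depends on how hard the examiner pulls. Standardisation reduces this but does not remove it.

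At stake second is who enters the comparison. If the arm is fixed before written consent, and someone who knows it takes part in consent, patients can be lost differently by arm. If someone who has seen past allocations also screens, the next allocation is partly predictable. Either route could reach the FJS even though patients complete it themselves.

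**Working it through.** The plan states no figure on this point, so the check is mainly a comparison of text.

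**1. Allocator against recorder, under each reading.**

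| Section followed | Allocates | Knows the arm | Assists with recording (3.9) |
|---|---|---|---|
| 3.4 | Fellow | Fellow; CI | RP and fellow |
| 5.0 | RP | Fellow and CI (through 3.6); RP unless the result is hidden from the RP | RP and fellow |

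In both rows the fellow knows the arm and assists. Only the second row puts the RP's blinding in doubt.

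**2. Do the safeguards close the gap?** Withholding the seed and screen shots protects against the CI foreseeing the sequence. Not reusing numbers keeps the blocks intact. Appendix 19.6 limits examiner influence on the tests. None of these separates the person who allocates from the person who records. The text does not say who holds the list during the trial. Section 10 says only that the listing of allocated groups is archived at the site, among the same documents as the case report forms.

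**3. Order of consent and allocation.** The explicit sequence in 3.4, 5.0 and the change-of-mind rule in 3.6 is: agreement, randomisation, written consent at preadmission. Section 6.5 then puts baseline after the consent form. So there is an interval in which an arm exists and written consent does not. Section 5.0 lets the study coordinator or a designated member of the surgical team take consent. When the CI is told the arm, relative to consent, is not stated.

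**4. Predictability for an allocator who also screens.** Section 5.0 lists the fellow and the RP among the screeners, and 3.6 fixes the block size at 4. A balanced block of 4 has 6 possible sequences, which gives 6 × 4 = 24 positions. Take someone who knows the block size and has seen the earlier allocations.
- Known with certainty: the fourth position in all 6 sequences, and the third in the 2 sequences that open with two alike. (6 + 2)/24 = 1/3.
- Best guess correct, by position: 1/2; 2/3; (1/3 × 1) + (2/3 × 1/2) = 2/3; 1. The average is (1/2 + 2/3 + 2/3 + 1)/4 = 17/24, or 71%, against 50% by chance.

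Someone who holds the list need not guess at all. This is a property of the design, not evidence that selection occurred.

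**5. Patients randomised who do not sign.** Section 6.3 defines the intention-to-treat (ITT) set as everyone randomised. Sections 3.6 and 5.0 send those who change their mind before consent to routine, non-study care. Section 5.1 excludes people unwilling to sign, so under 6.4 they would not be in the per-protocol set, which 6.2.1 makes primary. By 6.5 they would have no baseline. The plan does not say whether ITT includes them or how their change from baseline would be obtained.

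**The case against.** The strongest reply has five parts.

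- **Section 5.0 is the outlier.** Sections 3.4 and 3.6 both point to the fellow, and 5.0 itself refers to 3.6 for the method. The RP might trigger an allocation without seeing the result. This stands: that the RP knows the arm is a possibility under 5.0, not something the plan states. It does not help the fellow.
- **Assisting is vague, and roles may be set out elsewhere.** Section 3.9 does not say which measures either role records. Sections 3.2 and 3.3, the second on the investigational team, were not in the text available for this review and may assign duties. This stands as a limit. A reader might infer that allocator and assessor are definitely the same person. The text supports only that they are not shown to be separate. No team list can remove the conflict between 3.4 and 5.0.
- **The order is consistent.** A reader might infer that the protocol flatly contradicts itself on consent before or after randomisation. The two consent-first phrases do not establish that. Order of consent in 3.6 can mean verbal agreement, and 3.7 may only list two steps completed before surgery. Randomising before written consent remains a real design weakness.
- **The primary outcome is self-completed by blinded patients.** This is correct, and it is why the direct concern is confined to secondary outcomes.
- **Non-signers do not affect the primary result.** They would not be in the per-protocol set. A reader might infer that they certainly stay in ITT. That is one reading of 6.3, and the routine-care wording in 3.6 and 5.0 pulls against it.

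**Conclusion.** The point holds. The plan names two randomisers, has the fellow know every arm, and has the fellow help with recording that it calls blinded. Under 5.0 the same may be true of the RP. Assessor blinding is promised but not secured.

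The size of any bias cannot be derived from the documents. They give no assessor effect, no count of patients lost between allocation and consent, and no enrolment to date. Only planned milestones and an expected recruitment rate are stated. A reader might be tempted to quote an inflated false-positive rate or a shift in FJS points. Either would rest on an assumed assessor effect or an assumed one-sided loss with no anchor in the plan. The 1/3 and 71% above describe predictability only, and only for someone who knows the block size and sees past allocations.

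Nor does it follow that the FJS result is compromised. Its exposure is indirect and needs consent or screening staff who know, or can predict, the arm. The conclusion assumes that 3.3 contains no explicit separation of roles. If it does, the blinding concern narrows, but 3.4 and 5.0 must still be reconciled. This should be corrected, and it is not by itself a reason to doubt the primary comparison.

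**What to change.** 1. Name one allocator and list holder, the same in 3.4, 3.6 and 5.0. Remove that role, and anyone else who knows the arm, from eligibility screening, consent and outcome recording in 3.9 and 5.0.
2. State that outcomes are recorded only by existing staff who do not know the arm. Keep the allocation listing and form 19.8, which records the alignment method, from them. The visit forms in Appendix 19.1 have a field for who completed them, so use it to audit who has recorded outcomes so far. Report any outcome recorded by someone who knew the arm as not assessor-blinded.
3. State one order in 3.4, 3.6, 3.7 and 5.0: written consent and baseline, then release of the allocation, in time for the planning in Appendix 19.9. The preoperative form already has a field for the randomisation date, which helps in checking the order used so far.
4. Report by arm how many were randomised without signing consent, and state whether they belong to ITT, reconciling 6.3 with the change-of-mind rules in 3.6 and 5.0.

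The cost is protocol wording, a short audit and a re-split of duties. The surgeon learns the arm later. Section 3.7 has both plans built from the CT, but 19.9 bases the preoperative plan on the allocation. The interval from preadmission to surgery is not stated, so the site must confirm that release still fits. Section 8 mentions one full-time-equivalent RP, so a blinded recorder may be hard to find. Where none exists, the cost is reporting those outcomes as unblinded.

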5.1 Eligibility Criteria

The inclusion and exclusion criteria for all patients included in this study is shown below:

Inclusion Criteria

- Patient has symptomatic knee osteoarthritis requiring primary TKA
- Patient and surgeon are in agreement that TKA is the most appropriate treatment
- Patient is fit for surgical intervention following review by surgeon
- Patient is between 45-75 years of age at time of surgery, computer literate, and able to complete patient reported outcome measures independently.
- Patient must be capable of giving informed consent and agree to comply with the postoperative review program
- Patient must be a permanent resident in an area accessible to the study site
- Patient must have sufficient postoperative mobility to attend follow-up clinics and allow for radiographs to be taken
- Patient has tried non-pharmacologic therapy's including ; patient education, self-management programs, aerobic exercise, weight loss, physiotherapy and occupational therapy
- Patient has tried appropriate pharmacologic therapies including ; regular paracetamol and NSAIDS if appropriate

Exclusion Criteria

- Patient is not suitable for routine primary TKA. E.g. patient has ligament deficiency that requires a constrained prosthesis
- Interoperative requirement for a more constrained implant.
- Intraoperative requirement for the PCL to be released. These patients will be still included in the study, but analyzed with an intention to treat principal.
- Patient has bone loss that requires augmentation
- Patient requires revision surgery following previously failed correctional osteotomy or ipsilateral TKA (eg. Post high tibial or distal femoral osteotomy)
- Patient requires a polyethylene inset of 16mm or greater.
- Patient is immobile or has another neurological condition affecting musculoskeletal function
- Patient is less than 44 years of age or greater than 76 years of age
- Patient is a compensable patient. I.e. Worker's compensation claim or motor vehicle accident.
- Patient is already enrolled on another concurrent clinical trial
- Patient is unable or unwilling to sign the informed consent form specific to this study
- Patient is unable to attend the follow-up program
- Patient is non-resident in local area or expected to leave the catchment area postoperatively
- Patients who lacks capacity to provide consent, or the ability to understand the study protocol due to a cognitive condition (eg. Dementia)
- Patient is unable to communicate effectively in English.

6.0 Statistical Methods

6.1 Power / Sample size calculation

Primary Outcome measure: Functional outcome as assessed using the FJS score at two years following Mako-arm assisted TKA.

Using data from our initial cohort recording functional outcomes, the mean FJS score at 1 year in the mFA TKA was 59 (SD 6) and in the kFA TKA was 75 (SD 8). It is assumed that MA results will be no better than mFA results. The study was powered to demonstrate a 12 point difference in the Forgotten Joint score, which is the minimal clinical important change in the score. Using a one tailed analysis (assuming superior results with the kFA), an alpha value of 0.05 and power of 0.80, and accounting for expected drop-out rate of 10%, this study will need 100 patients to answer the study question.

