Limits are placed in Functional alignment to prevent the severely arthritic knee with attenuated ligaments being placed in extremes of alignment. Understanding the “safe zone” for functional alignment is important for patient selection, implant choice, extent of intraoperative deformity correction, and long-term follow up. Furthermore, some disease pathology such as bone tumors, previous trauma, and congenital deformities may be present in conjunction with the arthritic knee and will have altered the native alignment of the limb. In such cases, using functional alignment to reproduce the altered anatomical alignment and mechanical function may have a detrimental effect on knee mechanics and wear.

A preliminary series by the principal investigator involved 122 TKR with mFA and over 350 kFA aligned knees since the introduction of RATKA into my practice. In an initial cohort of patients with functional alignment substantial differences were seen in femoral and tibial component position depending on whether a mechanical or kinematic plan was used. The final HKA angle was not changed as the coronal limb alignment is dictated by the collateral ligaments. The femur was 2 degrees valgus and the tibia 4 degrees varus with the kinematic plan compared to a neutral femur and 2 degree varus tibia with a mechanical plan. These small changes in position effect the three-dimensional relationships of the implants with the soft tissues. The initial cohort showed improved outcomes with the KA plan. There were confounding factors in that the groups were sequential, with MA plan group forming part of the surgeon’s learning curve. For the planned study a KA plan will be used as superior results have been seen in this group in the initial series..

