2.1 Primary objective

- The primary objective of this study is to compare clinical outcomes at two years following surgery between FA TKA and MA TKA. The primary outcome measure for this study is the Forgotten Joint Score (FJS) at two years after surgery. The null hypothesis is that there is no difference in functional scores at two years following surgery between patients undergoing MA TKA (control group) versus FA TKA (investigation group). The hypothesis is that outcome measures obtained at two years after surgery in patients undergoing FA TKA are not achievable using MA TKA. Further PROMs will be used to further assess clinical outcomes including Forgotten Joint Score (FJS), Oxford Knee Score (OKS), Knee injury and osteoarthritis outcome Junior score (KOOS Jr), VAS Pain, and Kujala scores preoperatively and postoperatively at 3 months, 1 year and 2 years. Also health-related quality of life will be measured using European Quality of Life questionnaire with 5 dimensions for adults (EQ-5D-5L) preoperatively and postoperatively at 3 months, 1 year and 2 years. Range of movement (degrees) in knee joint during inpatient admission and postoperatively at 6 weeks, 3 months, 1 year and 2 years.

2.2 Secondary objectives The secondary objectives of the study are:

- Determine lower limb alignment achieved with both alignment techniques. Lower limb alignment as assessed using standing long leg x-rays performed postoperatively at 3 months. Measurements of the hip-knee-angle (HKA), medial proximal tibial angle (MPTA) and lateral distal femoral angle (LDFA). Also evidence of imbalance with implant lift off will be measured.

- Determine if there are any differences in analgesic requirements based on alignment method used. Analgesia requirements during inpatient admission and postoperatively at 6 weeks, 3 months, 1 year and 2 years will be measured.
- Determine whether alignment method utilized has an effect on the sagittal stability of the TKA. Assessment of sagittal stability at Preop, 3 months, 1 year and 2 years will be undertaken with an arthrometer “Lachmeter”.
- Determine whether alignment method utilized has an effect on functional outcomes. This will be assessed by a combination of
 - Maximum voluntary isometric force using a hand-held dynamometer at Preop, 3 months, 1 year and 2 years.
 - Sit to stand values as measure of function at Preop, 3 months, 1 year and 2 years.

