3.5 Sample Size In total, 100 patients will be enrolled in a 1:1 ratio between the two treatment groups. This will ensure that the minimum of 90 patients required to answer the study question are followed up for the duration of the study. The enrolment goal is to have at least 45 patients in each of the two treatment groups completing the study. Sample size calculation and statistical analysis are more comprehensively detailed in section 6.

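### Section 6.1's quoted inputs need 6 to 7 patients per arm, not 45, and it sizes one-tailed while section 6.2.1 uses a two-sided 95% interval

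*Combined protocol and SAP*

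**What the plan says.** Section 6.1 defines the outcome used for sizing as "Functional outcome as assessed using the FJS score at two years following Mako-arm assisted TKA". Its only variability figures are one-year results from the investigators' earlier cohort: "the mean FJS score at 1 year in the mFA TKA was 59 (SD 6) and in the kFA TKA was 75 (SD 8"). It assumes that mechanical alignment will do no better than the mFA knees, and gives no separate mean or SD for it.

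The target is then set: "The study was powered to demonstrate a 12 point difference in the Forgotten Joint score". The error rates follow: "Using a one tailed analysis (assuming superior results with the kFA), an alpha value of 0.05 and power of 0.80". With 10% drop-out, section 6.1 concludes that 100 patients are needed.

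Section 3.5 refers to "the minimum of 90 patients required to answer the study question" and adds: "The enrolment goal is to have at least 45 patients in each of the two treatment groups completing the study".

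Section 2.1 sets the hypothesis being tested: "The null hypothesis is that there is no difference in functional scores at two years following surgery". Section 6.2.1 specifies the primary analysis as a two-sided 95% confidence interval for the between-group difference in change from baseline, and in its last sentence speaks of percentage change. Section 6.2.2, on secondary endpoints, says that p-values will be two-sided.

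**The concern.** A 12-point difference with SDs of 6 and 8 is a standardised effect of 1.5 or more. An effect that large needs only a handful of patients per arm, so 45 per arm cannot follow from the figures printed beside it. Either another SD or another hypothesis was used and left out, or the calculation is wrong.

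The test used for sizing is also not the test used for analysis. A two-sided 95% interval that excludes zero in the favourable direction corresponds to one-sided 0.025, not 0.05. A sample sized to give exactly 80% power at one-sided 0.05 gives less than that under section 6.2.1.

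What is at stake is how the result is read. If the SD really is about 7, a null result at 45 per arm would rule out quite small differences. If it is about 23, a true 12-point difference would be missed roughly three times in ten. The plan does not let a reader tell these cases apart.

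**Working it through.** **Inputs.** From section 6.1: SDs 6 and 8, means 59 and 75 (observed difference 16), target difference 12, one-tailed alpha 0.05, power 0.80, drop-out 10%. From section 3.5: 1:1 allocation, 90 completers, 45 per arm. From section 2.1: a null of no difference. From section 6.2.1: a two-sided 95% interval.

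**Drop-out step.** 90 / (1 − 0.10) = 100. This is the only part of the plan's figure that reproduces.

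**Patients per arm for 12 points against zero.** The equal-variance average SD is √((36 + 64)/2) = 7.07. The normal approximation is n = 2·SD²·(z₁₋α + z₁₋β)²/Δ². One-sided, with 1.645 + 0.842 = 2.487:

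- SD 7.07: 2 × 50 × 2.487² / 144 = 4.29, so 5 per arm.
- SD 8: 2 × 64 × 2.487² / 144 = 5.50, so 6 per arm.

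Exact power uses the noncentral t with 2n − 2 degrees of freedom and noncentrality Δ/(SD·√(2/n)). It gives slightly more:

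| SD | One-sided n per arm (power) | Two-sided n per arm |
|---|---|---|
| 7.07 | 6 (0.862) | 7 |
| 8 | 7 (0.841) | 9 |

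One-sided, that is 12 to 14 completers: 12/0.9 gives 14 enrolled and 14/0.9 gives 16, against 100 stated. Taking the smaller SD of 6 alone lowers the figures to 4 one-sided and 6 two-sided. Powering on the observed 16 points instead needs 4 per arm one-sided, or 5 to 6 two-sided (SD 7.07 to 8).

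**What 45 per arm delivers at the quoted SDs.** Power for 12 points exceeds 0.9999, one- or two-sided, at any SD from 6 to 8. The difference detectable with 80% power, two-sided, is 3.6 points (SD 6), 4.2 (SD 7.07) or 4.8 (SD 8).

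**Solving back for the SD.** For 45 per arm to give 80% power for 12 points against zero, the SD must be 22.7 (one-sided) or 20.1 (two-sided). That is about three times the quoted values.

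**Cost of the one-tailed/two-sided mismatch.** At SD 22.7 and 45 per arm, two-sided power is 0.698. Restoring 80% would take 58 per arm. As assumed sensitivity values only, two-sided power for 12 points at 45 per arm is 0.80 at SD 20 and 0.61 at SD 25.

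**A reading that does reach 45.** Suppose a true difference of 16 were tested against a margin of 12, an effect of 4. The Introduction says that the earlier series "involved 122 TKR with mFA and over 350 kFA aligned knees". Weighting the SDs by 122 and 350 gives √((121 × 36 + 349 × 64)/470) = 7.54, and the one-sided requirement is then 45 per arm (power 0.803). It is sensitive to the SD:

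| SD | One-sided n per arm | Two-sided n per arm | Two-sided power at 45 per arm |
|---|---|---|---|
| 7.07 | 40 | 51 | 0.756 |
| 7.54 | 45 | 57 | 0.702 |
| 8 | 51 | 64 | 0.650 |

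**The analysed variable.** No SD for change from baseline is given. If the baseline SD equalled the follow-up SD and the two were uncorrelated (both assumptions), the SD of change would be 7.07·√2 = 10.0 or 8·√2 = 11.3. The two-sided requirement for 12 points would be 12 or 15 per arm, still far from 45. The detectable difference at 45 per arm would be 6.0 or 6.8 points.

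**The case against.** The strongest reply is that section 6.1 never says that 6 and 8 went into the formula. They are reported as cohort results for mFA and kFA knees, and the control arm is mechanical alignment, for which no SD is given. That is fair. It means the sizing SD is missing rather than shown to be wrong. But these are the only SDs in the plan, they sit in the power paragraph, and no combination of them tested against zero comes near 45.

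A second reply is that the margin reading explains the figure. It may be a coincidence. Sections 2.1, 6.1 and 6.2.1 state no margin, section 2.1 states a null of no difference, and the Introduction gives more than 350 knees without saying how many had a one-year FJS. If it is the true basis, it has to be written down, and two-sided power is still about 70%.

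A third reply is that nothing shows the trial to be underpowered: with the quoted SDs and the stated null, power exceeds 99.9%. This stands. The 70% figure is conditional on one of the two unstated routes. It is also true that section 6.2.1 gives an interval without an explicit decision rule, so the mismatch could in principle be removed by moving the analysis to one-sided 0.05. Moving the sizing instead is more natural, because the stated null is no difference and section 6.2.2 also reports two-sided p-values.

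**Conclusion.** The concern holds. As written, the inputs in section 6.1 need 6 to 7 patients per arm one-sided, or 7 to 9 two-sided, against the 45 per arm that sections 3.5 and 6.1 rest on. That assumes a two-sample t-test against zero with an SD of 7.07 to 8. The gap is at least six-fold one-sided and five-fold two-sided, too large for rounding or choice of formula. The conflict between one-tailed sizing and a two-sided 95% interval is explicit and needs no assumption.

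The finding is that the sample size and its 80% power are unsupported, not that the trial is the wrong size. It gives no ground for cutting enrolment: an unstated SD of 20 to 23 would make 45 per arm about right for one test or the other. If the sizing was one-sided by either unstated route, power under the planned two-sided analysis is about 70%.

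**What to change.** Keep enrolment at 100 and revise sections 6.1 and 3.5 as follows.

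- State the SD, its source, the formula and any margin that gave 45 per arm. Remove the implication that the quoted one-year figures by themselves require 90 completers. If a 12-point margin was intended, state it in sections 2.1, 6.1 and 6.2.1.
- Use two-sided alpha 0.05 in section 6.1, to match section 6.2.1.
- Settle whether the primary variable is the two-year FJS, its change from baseline or its percentage change. Then give the power, or the difference detectable at 80% power, for that variable at 45 evaluable patients per arm over a range of SDs. Label any SD without a documented source as an assumed sensitivity value.

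Suggested wording: *With 45 evaluable patients per arm and two-sided alpha 0.05, the trial has 80% power to detect X points in [primary variable] if the SD is Y (source).*

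The cost is protocol and SAP wording only. The downside is that the stated power may look less favourable. Against zero, two-sided power for 12 points falls below 80% only if the SD exceeds about 20; on the margin reading it is about 70% at SD 7.54.
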